8.2.12. Deterioration in LRTI Symptoms at D5V Using ATP-5 Analysis Population

A forest plot of 95% CIs for the risk difference of deterioration in any qualifying symptom (cough, sputum production, chest pain, or difficulty breathing) at D5V compared to baseline will be analyzed in subjects having the symptom at baseline will be provided in [Figure 12](#) using ATP-5 Analysis Population. Results will also be reported in [Table 39](#), and tests for differences in proportions between treatment arms will be given by Fisher's exact tests. Since Fisher's test cannot be inverted, there is no corresponding CI. Therefore, the Miettinen–Nurminen method will be used to compute all 95% CIs for risk differences. Note that the CI results might not be consistent with the p-value from Fisher's exact test.

8.2.13. New occurrence of Vital Sign Abnormality or Fever at D5V Using ATP-5 Analysis Population

Using ATP-5, a forest plot of 95% CIs for the risk difference of new vital sign abnormality at D5V compared to baseline or fever in the 24 hours preceding or at D5V will be provided in [Figure 14](#). Results will also be reported in [Table 42](#) to include a p-value from Fisher's exact test. Since Fisher's test cannot be inverted, there is no corresponding CI. Therefore, the Miettinen–Nurminen method will be used to compute all 95% CIs for risk differences. Note that the CI results might not be consistent with the p-value from Fisher's exact test.

8.3. Exploratory Efficacy Analyses

8.3.1. Analysis of PCT Levels at D5V Using ATP-5 Analysis Population

Using the ATP-5 analysis population, mean changes in PCT levels at D5V relative to baseline will be computed for placebo versus azithromycin, in addition to an estimated difference in mean PCT changes from

baseline and associated 95% CI based using bootstrap with 10000 samples. The bootstrap CI estimates will use the 2.5th and 97.5th percentiles of samples obtained by repeatedly re-sampling the empirical distribution of PCT changes from baseline with replacement for each treatment group. A similar approach will be used to estimate 95% CI for difference in mean PCT changes from baseline for placebo relative to azithromycin based. Significance of a difference in mean PCT changes for placebo compared to azithromycin will be tested by a Wilcoxon test and results will be reported in [Table 62](#) for all subjects and separately for subjects with clinical failure and clinical improvement. As the limit of quantitation is 0.05, PCT values reported as <0.05 will be imputed as half the limit of quantitation (i.e; 0.025) for this analysis. Individual subject PCT levels are provided in [Listing 12](#).

8.3.2. Association of Changes in PCT Levels at D5V and Clinical Improvement Using ATP-5 Analysis Population

The relationship between changes in PCT levels at D5V relative to baseline and clinical improvement at D5V will be assessed using logistic regression adjusting for treatment assignment and centered study day of D5V as covariates. Note that PCT values reported as <0.05 will be imputed as half the limit of quantitation (i.e; 0.025) for this analysis. Results will be reported in [Table 63](#).

8.3.3. Analysis of DOOR at D11V Using ITT and ATP-11 Analysis Populations

Analysis of DOOR at D11V will be performed using ITT and ATP-11 analysis populations separately and using similar methods as in Section 8.2.8. Results will be reported in [Table 46](#) for ITT and [Table 47](#) for ATP-11. Results from a sensitivity analysis using ATP-11 population with complete data will be reported in [Table 48](#). Summaries of OCO, a component of DOOR will also be analyzed. Number and percentage of subjects in each OCO category at D11V along with its 95% CI calculated using the Wilson method will be presented in [Table 49](#) for the ITT analysis population, [Table 51](#) for ATP-11 analysis population, and graphically in [Figure 16](#). A cumulative distribution function of these OCOs at D11V will also be presented in [Figure 19](#) for the ITT analysis population and [Figure 20](#) for the ATP-5 analysis population.

8.3.4. Analysis of Solicited Events at D11V Using ATP-11 Analysis Population

Results of the analysis of solicited events at D11V, a component of DOOR, will be presented using forest plots of 95% CIs for the risk difference of placebo compared to azithromycin of each solicited event and the risk difference for placebo compared to azithromycin of any solicited, for each severity threshold (mild or greater, moderate or greater, or severe) in [Figure 5](#), [Figure 6](#), and [Figure 7](#). Results will also be reported in [Table 59](#), [Table 60](#), and [Table 61](#), and tests for differences in proportions between treatment arms will be given by Fisher's exact tests. The Miettinen–Nurminen method will be used to compute all 95% CIs for risk differences.

8.3.5. Analysis of Medically Attended Events at D11V Using ATP-11 Analysis Populations

A forest plot of 95% CIs for the risk difference for placebo compared to azithromycin of one or more visits to an ED, one or more visits to an outpatient clinic, or one or more visits to an urgent care center or one or more hospitalizations for persistent or worsening LRTI at any time after randomization will be produced for D11V using ATP-11 analysis population in [Figure 9](#) and results will also be presented in [Table 44](#) to include a p-value from Fisher's exact test. The Miettinen–Nurminen method will be used to compute all 95% CIs for risk differences.

8.3.6. Improvement in Qualifying Symptoms or Vital Signs at D11V Using ATP-11 Analysis Population

The proportions of subjects exhibiting improvement in any symptom, any symptom or fever, at least two symptom, and one qualifying symptom (cough, sputum production, chest pain, or difficulty breathing) or fever at D11V compared to baseline will be computed for placebo versus azithromycin along with associated 95% CIs using ATP-11 population. A forest plot of 95% CIs for the difference for placebo compared to azithromycin in proportions of subjects with improvement any symptom or fever, any symptom, each individual symptom or fever will be provided in [Figure 11](#). Results will also be reported in [Table 35](#), and tests for differences in proportions between treatment arms will be given by Fisher's exact tests. The Miettinen–Nurminen method will be used to compute all 95% CIs for risk differences for placebo compared to azithromycin.

8.3.7. Deterioration in LRTI Symptoms at D11V Using ATP-11 Analysis Population

A forest plot of 95% CIs for the risk difference for placebo compared to azithromycin of deterioration in any qualifying symptom and in each symptom individually (cough, sputum production, chest pain, or difficulty breathing) at D5V compared to baseline will be analyzed in subjects having the symptom at baseline will be provided in [Figure 13](#) using ATP-5 Analysis Population. Results will also be reported in [Table 40](#), and tests for differences in proportions between treatment arms will be given by Fisher's exact tests. The Miettinen–Nurminen method will be used to compute all 95% CIs for risk differences.

8.3.8. New occurrence of Fever at D11V Using ATP-11 Analysis Population

Using ATP-11, a forest plot of 95% CIs for the risk difference of fever in the 24 hours preceding or at D11V will be provided in [Figure 15](#). Results of fever at D11V will also be reported in [Table 45](#). Tests for differences in proportions between treatment arms will be given by Fisher's exact tests. The Miettinen–Nurminen method will be used to compute all 95% CIs for risk differences.

8.3.9. Bivariate Analysis of DOOR and Number of Days of Antibiotics Use at D5V and D11V

In addition to the DOOR analyses described in Section 8.2.8, a two-dimensional analysis of the DOOR probability and difference in the mean duration of antibiotic use in the two treatment groups will also be performed at D5V. Only subjects with non-missing DOOR and number of days on antibiotics will be included in these analyses. The horizontal axis is the DOOR probability (probability of a more desirable outcome when assigned to placebo vs. azithromycin) based on the ordinal DOOR outcome ignoring the duration of antibiotic use. The vertical axis is the difference in the means of the observed (outcome not assignment) duration of antibiotic use (placebo minus azithromycin). A result in the lower right quadrant represents more desirable results for placebo, while a result in the upper left represents more desirable for azithromycin. The other two quadrants represent tradeoffs for clinical outcomes and antibiotic use.

1000 bootstrap samples will be generated by resampling with replacement from the empirical distribution of DOOR and number of days of antibiotics use at D5V. The DOOR probability and mean difference in the number of days of antibiotics use will be estimated using the bootstrap samples and plotted as a scatter plot. A 95% joint region of DOOR probability and duration for antibiotic will be constructed first using a parametric method and repeated using a nonparametric method. The parametric method will estimate the confidence region using the ellipse method from the CAR R package which uses a bivariate normal distribution. The nonparametric will use distribution-free approach implemented in the distfree.cr R package proposed by Hu and Yang (2013) in [12]. Marginal distributions of DOOR probability and difference in duration of antibiotics will be provided. To confirm the robustness of these results, these plots will be regenerated using 2000

bootstrap samples and all results will be reported in [Figure 21](#) to include subjects in ITT population with non-missing DOOR and non-missing number of days of antibiotics use at D5V. These calculations will be repeated for D11V and results will be reported in [Figure 22](#) to include subjects in the ITT population with non-missing DOOR and non-missing number of days of antibiotics use at D11V.

8.3.10. Longitudinal Analysis of Clinical Improvement using DOOR for ITT Analysis Population

In order to compare patterns of clinical improvement over time, multiple longitudinal analyses based on DOOR will be performed. For each of these analyses, a different definition of DOOR will be used.

8.3.10.1. Number of Times Clinical Improvement Was Achieved across D5V, D11V, and D28V

The first longitudinal analysis uses the number of days clinical improvement was achieved across D5V, D11V, and D28V to define DOOR. The number of times clinical improvement was achieved across the three timepoints for the ITT population will be calculated as:

- 0: No clinical improvement at any of the three timepoints
- 1: Clinical improvement achieved at one of the timepoints
- 2: Clinical improvement achieved at two of the timepoints
- 3: Clinical improvement achieved at all three timepoints
- Missing: Clinical improvement missing for at least one of the timepoints

A summary table of frequency counts and percentages of subjects in each of the above options (0,1,2,3, Missing) across the two treatment groups will be provided in [Table 52](#).

8.3.10.2. DOOR Analysis Based on the Number of Times Clinical Improvement Was Achieved across D5V, D11V, and D28V

To construct DOOR for this analysis, an observed number of times clinical improvement was achieved across the three timepoints will first be calculated for each subject. This calculation will be based on subjects with non-missing clinical improvement for at least one timepoint, and the observed count for each subject will ignore missingness of clinical improvement for any of the timepoints. Next, subjects will be ranked based on the observed number of times clinical improvement was achieved first without tie-breaking and repeated by using days of antibiotic use as a tie-breaker.

For the DOOR analysis without tie-breaking, subjects with a higher observed number of times clinical improvement was achieved will be assigned a higher (better) rank.

For the DOOR analysis using days of antibiotics use as a tie-breaker, subjects will be assigned DOOR according to the following two rules:

- When comparing two subjects with different observed number of times clinical improvement was achieved, the subject with a higher number of times receives a higher rank.
- When comparing two subjects with the same observed number of times clinical improvement was achieved, the subject with fewer days of antibiotic use receives a higher rank.

The null hypothesis corresponding to this analysis is:

H0: The sum of the probability that a subject assigned to placebo will have a higher DOOR Visit than if assigned to the Azithromycin plus one-half the probability of equal DOORs is 50% (i.e., no difference in DOOR).

The above null hypothesis can be tested using a Mann-Whitney U Test [1].

The analysis of this new DOOR will use the same approach as that described in Section 8.2.8 to estimate Prob (higher DOOR in placebo compared to Azithromycin) + $\frac{1}{2}$ Prob(no difference in DOOR). The Mann Whitney test will be used to test the differences.

Results of this DOOR analysis will be reported in Table 53.

8.3.10.3. DOOR Analysis Based on the Average of Daily Ordinal Clinical Outcomes from Study Day 1 to Study Day 11

The second longitudinal analysis will use average of daily OCOs from Day 1 to Day 11 to construct DOOR.

8.3.10.3.1. Daily Ordinal Clinical Outcomes from Study Day 1 to Study Day 11

Using similar definitions for clinical improvement and most severe solicited event as those provided in Section 6.5, daily values of clinical improvement status, maximum severity of solicited symptoms, and presence of any medically attended visits will be calculated for each day. Vital signs will be excluded from the definition of daily clinical improvement since they were not collected daily. These values will then be used to calculate a daily OCO for each subject as follows:

If the subject died at any point of study participation, then OCO will be 8.

Else if the subject has missing clinical improvement at that day then OCO will be missing.

Else if the subject did not have clinical improvement at day and was hospitalized at that day then OCO will be 7.

Else if the subject did not have clinical improvement at that day with ED, outpatient clinic, or urgent care visit but was not hospitalized that day then OCO will be 6.

Else if the subject did not have clinical improvement at that day and did not have any medically attended events for that day then OCO will be 5.

Else if the subject has missing most severe solicited event at that day as defined in Section 6.5.3 then OCO will be missing.

Else if the subject had clinical improvement at that day and a most severe solicited event of grade 3 for that day then OCO at that day will be 4.

Else if the subject had clinical improvement at that day and a most severe solicited event of grade 2 for that day then OCO will be 3.

Else if the subject had clinical improvement at that day and a most severe solicited event of grade 1 for that day then OCO will be 2.

Else if the subject had clinical improvement at that day and did not experience any solicited event for that day (i.e; the most severe solicited event for that day is of grade 0) then OCO will be 1.

Note that in some cases OCO can be defined even if some components are missing. For instance, if a subject had record of receipt of study product and did not have clinical improvement that day, OCO for that day would still be defined even if most severe solicited event was missing since the above algorithm doesn't take solicited events severity into account for OCO levels 5, 6, 7, and 8.

The daily OCOs will be presented using two graphical presentations. First a bar plot of the percentage of subjects falling in each of the daily OCO categories from study Day 1 until study Day 11 will be presented by study day and separately for each treatment group for the ITT population in [Figure 23](#). The missing OCO category will also be added to the figure. Second, a heatmap plot of individual subject's OCO will be plotted for each day, and separate plots will be generated for the two treatment groups as presented in [Figure 25](#). Subjects will be ordered in the heatmap figure such that subjects with the best outcome (i.e; lower values of OCO) appear at the bottom and subjects with the worst outcome or missing OCO appear at the top.

8.3.10.3.2. DOOR Analysis Daily Ordinal Clinical Outcomes from Study Day 1 to Study Day 11

To construct DOOR for this analysis, an average of observed OCO from study Day 1 to study Day 11 will be calculated for each subject ignoring missingness of data at some of the timepoints. This calculation will be based on subjects with non-missing OCO for at least one timepoint, and the average OCO calculation for each subject will ignore missingness of OCO for any of the timepoints. Next, subjects will be ranked based on their average OCO without tie-breaking.

For the DOOR analysis without tie-breaking, subjects will be ranked such that subjects with a lower average OCO are assigned a higher (better) rank while subjects with higher average OCO are assigned a lower (worse) rank.

The null hypothesis corresponding to this analysis is:

H0: The sum of the probability that a subject assigned to placebo will have a higher DOOR Visit than if assigned to the Azithromycin plus one-half the probability of equal DOORs is 50% (i.e., no difference in DOOR).

The above null hypothesis can be tested using a Mann-Whitney U Test [1].

The analysis of this new DOOR will use the same approach as that described in Section 8.2.8 to estimate Prob (higher DOOR in placebo compared to Azithromycin) + $\frac{1}{2}$ Prob(no difference in DOOR). The Mann Whitney test will be used to test the differences.

Results of this DOOR analysis will be reported in [Table 54](#).

8.3.10.4. DOOR Analysis Based on the Average of Ordinal Clinical Outcomes from D5V, D11V, and D28V

The second longitudinal analysis will use average of OCOs from D5V, D11V, and D28V to construct DOOR.

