8.3.10.4.2. DOOR Analysis Based on Ordinal Clinical Outcomes from D5V, D11V, and D11V

To construct DOOR for this analysis, an average of observed OCO across the three timepoints will be calculated for each subject ignoring missingness of data at some of the timepoints. This calculation will be based on subjects with non-missing OCO for at least one timepoint, and the average OCO calculation for each subject will ignore missingness of OCO for any of the timepoints. Next, subjects will be ranked based on their average OCO without tie-breaking.

For the DOOR analysis without tie-breaking, subjects will be ranked such that subjects with a lower average OCO are assigned a higher (better) rank while subjects with higher average ordinal clinical outcome are assigned a lower (worse) rank.

The null hypothesis corresponding to this analysis is:

H0: The sum of the probability that a subject assigned to placebo will have a higher DOOR Visit than if assigned to the Azithromycin plus one-half the probability of equal DOORs is 50% (i.e., no difference in DOOR).

The above null hypothesis can be tested using a Mann-Whitney U Test [1].

The analysis of this new DOOR will use the same approach as that described in Section 8.2.8 to estimate Prob (higher DOOR in placebo compared to Azithromycin) + $\frac{1}{2}$ Prob(no difference in DOOR). The Mann Whitney test will be used to test the differences.

Results of this DOOR analysis will be reported in Table 55.

8.3.11. Association PCT Level at Screening and Detection of a Viral or Bacterial Pathogen

The relationship between PCT level at screening and detection of a viral pathogen will be assessed using logistic regression. Analysis will be repeated with detection of a bacterial pathogen as the outcome. The Results will be reported in Table 64. Individual listing of pathogens detected is provided in Listing 22.

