Missing ^b	xx	xx (xx, xx)	xx	xx (xx, xx)

N = Number of subjects in the ITT Population in the given treatment group.

^a95% CI estimated using the Wilson Method.

^bNumber of subjects missing clinical improvement at all three timepoints (D5V, D11V, D28V) will be classified as missing.

Table 53: ITT Analysis of DOOR Based on Number of Times Clinical Improvement was Achieved Across D5V, D11V, and D28V - ITT Analysis Population with Complete Data

Tie-Breaking	Statistic	Value
No tie-breaking	Subjects with non-missing DOOR– n (%)	x (x)
	Pr(Higher DOOR in Placebo Arm) ^a (95% CI) ^b	x.xx (x.xx, x.xx)
	P-value ^c	x.xxx
Duration of antibiotic use as tie-breaker	Subjects with non-missing DOOR– n (%)	x (x)
	Pr(Higher DOOR in Placebo Arm) ^a (95% CI) ^b	x.xx (x.xx, x.xx)
	P-value ^c	x.xxx

Note: DOOR was calculated based on subjects with non-missing clinical improvement for at least one of the timepoints.
^aProbability of Higher DOOR in Placebo Arm + 0.5 Probability of Equal DOOR. CI obtained through inversion of the F-test used to compute the p-value.
^bObtained through using inversion of the Mann-Whitney U test with a normal approximation and assuming the null hypothesis distribution variance provided in Section 8.2.8 correcting for ties.
^cP-value obtained by Mann-Whitney U Test. P-value boundary of 0.05 is used to conclude statistical significance.

Table 54: ITT Analysis of DOOR Based on Average Ordinal Clinical Outcome from Study Day 1 Through Study Day 11 - ITT Analysis Population with Complete Data

Statistic	Value
Subjects with non-missing DOOR– n (%)	x (x)
Pr(Higher DOOR in Placebo Arm) ^a (95% CI) ^b	x.xx (x.xx, x.xx)
P-value ^c	x.xxx

Note: DOOR was calculated based on subjects with non-missing OCO at atleast one of the timepoints. Missing values were ignored when calculating average OCO.
 
^aProbability of Higher DOOR in Placebo Arm + 0.5 Probability of Equal DOOR. CI obtained through inversion of the F-test used to compute the p-value.
 
^bObtained through using inversion of the Mann-Whitney U test with a normal approximation and assuming the null hypothesis distribution variance provided in Section 8.2.8 correcting for ties.
 
^cP-value obtained by Mann-Whitney U Test. P-value boundary of 0.05 is used to conclude statistical significance.
	

Table 55: ITT Analysis of DOOR Based on Average Ordinal Clinical Outcome from D5V, D11V, and D28V - ITT Analysis Population with Complete Data

Statistic	Value

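### The count-based longitudinal DOOR (SAP 8.3.10.2) scores a missed visit in a partly observed subject as non-improvement, so unequal partial missingness between arms biases Table 53

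*SAP*

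**What the plan says.** SAP 8.3.10.2 builds a ranking from the number of times, out of three (D5V, D11V, D28V), that a subject achieved clinical improvement.

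- **Who is ranked:** "This calculation will be based on subjects with non-missing clinical improvement for at least one timepoint".
- **How gaps are treated:** "the observed count for each subject will ignore missingness of clinical improvement for any of the timepoints".
- **Direction:** "subjects with a higher observed number of times clinical improvement was achieved will be assigned a higher (better) rank".
- **Test:** "The Mann Whitney test will be used to test the differences", against a DOOR probability of 50%. A Table 53 footnote adds that "P-value boundary of 0.05 is used to conclude statistical significance".

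The ranking is run without a tie-breaker and again with days of antibiotic use as tie-breaker. The note to Table 53 repeats the one-timepoint rule, although the table title describes the population as having complete data.

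Two neighbouring passages differ. The DOOR in 8.3.10.4.2 uses an average: "the average OCO calculation for each subject will ignore missingness of OCO for any of the timepoints". The descriptive count in 8.3.10.1 has its own category, "Missing: Clinical improvement missing for at least one of the timepoints", whereas footnote b of Table 52 reserves that category for subjects missing all three timepoints.

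**The concern.** A raw count and an average treat a gap differently. An average drops the missed visit from numerator and denominator. A count drops it only from the numerator, because its ceiling stays at three. A subject improved at the only visit seen scores 1 and ties with a subject seen three times who improved once. A subject improved at both of two observed visits ranks below one improved at all three.

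If the arms differ in how often visits are missed among partly observed subjects, the count differs between arms even when the clinical course is the same. Table 53 would then report a DOOR probability, confidence interval and p-value that mix retention with clinical outcome, and the table alone would not separate them. SAP 3.3.1 adds to the missingness, since out-of-window visits are set to missing in the ITT analysis.

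**Working it through.** **Inputs from the documents.** 337 per arm (Protocol 5); D5V improvement 57.6% in each group (SAP 5); two-sided test at 0.05 (Protocol 11.4); tie-corrected Mann-Whitney variance (SAP 8.2.8).

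**Assumptions, because the documents give no figures.** D11V and D28V improvement of 75% and 85%, identical in both arms; within-subject correlation of outcomes; missingness by arm, unrelated to outcome. Placebo is labelled as the arm with more missing visits; swapping the labels reverses the direction.

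**Reference point.** The plan's own figure is a null DOOR probability of 0.50 tested at 0.05. With equal missingness (16.9% per visit in both arms) the calculation returns 0.500 and a rejection rate of 0.050, so the rule causes no harm in that case.

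**One case by hand: 20% versus 14% missing at every visit, outcomes uncorrelated.** A visit adds 1 to the count with probability p(1 − m).

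- Placebo: 0.576 × 0.80 = 0.4608; 0.75 × 0.80 = 0.600; 0.85 × 0.80 = 0.680.
- Azithromycin: 0.576 × 0.86 = 0.4954; 0.75 × 0.86 = 0.645; 0.85 × 0.86 = 0.731.
- All three visits missing, hence excluded: 0.20³ = 0.008 and 0.14³ = 0.0027.
- Count 3, placebo: 0.4608 × 0.600 × 0.680 / 0.992 = 0.1895. Count 0, placebo: (0.5392 × 0.400 × 0.320 − 0.008) / 0.992 = 0.0615.

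The distributions over counts 0/1/2/3 are:

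- placebo 0.0615 / 0.3117 / 0.4373 / 0.1895
- azithromycin 0.0456 / 0.2665 / 0.4537 / 0.2342

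P(placebo higher) = 0.3117 × 0.0456 + 0.4373 × 0.3121 + 0.1895 × 0.7658 = 0.296. P(tie) = 0.0028 + 0.0831 + 0.1984 + 0.0444 = 0.329. The DOOR probability is 0.296 + 0.329/2 = 0.460, with no treatment effect.

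The numbers ranked are 337 × 0.992 = 334.3 and 337 × 0.9973 = 336.1. The cubes of the pooled proportions sum to 0.122, so the standard error is √[(1 − 0.122) × 671.4 / (12 × 334.3 × 336.1)] = 0.0209. The shift is −0.040/0.0209 = −1.91 standard errors, and Φ(−1.96 + 1.91) ≈ 0.48. Simulation of this case gives 47%.

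**Other patterns**, 337 per arm, no true effect, no tie-breaker (approximate simulated ranges):

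| Missing, placebo vs azithromycin | False rejection |
|---|---|
| 20% vs 14% at every visit | 40–47% |
| 22% vs 12% at every visit | 80–89% |
| 10-point gap at one visit only | 13–23% |
| Monotone 5/10/20% vs 5/8/10% | 27–35% |
| Monotone 14/17/20% vs 10/12/14% | about 6% |

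The higher figures in the first two rows belong to uncorrelated outcomes. The monotone rows show what drives the result. In the fourth row the share of subjects with some but not all visits missing is 20 − 5 = 15% against 10 − 5 = 5%. In the last row it is 20 − 14 = 6% against 14 − 10 = 4%; most of the imbalance there sits in subjects missing everything, who are not ranked.

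**Sensitivity to the assumed rates.** With flat 57.6%, 57.6/70/80% or 57.6/75/90% and latent correlation 0.3–0.6, per-visit gaps of 2, 5 and 10 points give false rejection of 7–10%, 16–36% and 49–90%.

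**After the change.** Ranking on the proportion of observed visits with improvement gives about 4–9% across the scenarios in the table.

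**Table 52.** At an assumed 17% missing independently at each visit, the 8.3.10.1 definition classes 1 − 0.83³ = 43% of subjects as missing; footnote b classes 0.17³ = 0.5%.

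**The case against.** The strongest reply is that nothing in the documents predicts unequal missingness. The trial is double-blind, and the planned loss is the same 16.9% in each group. That figure concerns eligibility for ATP-5, so it is only a proxy for missed visits. Equal missingness leaves the test at its level, and Table 20 will show missing clinical improvement by arm at all three visits. Tables 21, 23 and 25 give multiply imputed estimates at the same visits, so an artefact in Table 53 could be cross-checked. All of this stands. It limits the consequence but does not change the scoring rule.

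A reader might infer that every missing visit is scored as a failure, or that any imbalance produces a false effect. The text does not support either: subjects missing all three visits are excluded, and some dropout patterns leave the error rate close to nominal.

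It could also be said that 8.4.1 promises multiple imputation for all ITT analyses, which would fill the gaps. But 8.3.10.2 gives its own rule for gaps and does not call for imputed visits. Its reference to the 8.2.8 approach does not help either, because a subject with one observed visit already has a non-missing DOOR.

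Finally, averaging over observed timepoints is not free of bias, since the average still depends on which timepoints were observed. That is true, and it is the stated downside of the fix.

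**Conclusion.** The point holds for partly observed subjects. Under 8.3.10.2 as written, their missed visits count as non-improvement, and a between-arm difference in partial missingness biases the Table 53 DOOR probability and p-value against the arm with more of it. The size depends on the pattern, from about 6% to 80–89% false rejection in the scenarios above. It rests on assumed D11V and D28V rates, outcome correlation and missingness by arm. The percentages are for the ranking without tie-breaker; the tie-broken version uses the same count.

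A reader might go further and infer that the trial's conclusion is at risk. It is not: SAP 8.1.1 reserves the non-inferiority conclusion for the primary analysis, and this is one of several added exploratory analyses without multiplicity correction.

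The Table 52 conflict is a separate matter of definition in a descriptive table. The title of Table 53 likewise disagrees with its own note.

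**What to change.** In 8.3.10.2, rank on the proportion of observed visits with clinical improvement, in line with the averaging in 8.3.10.4. This is one derivation line and needs no new data. Its downside is a small residual bias when arms differ in which visit is missing, because improvement rates are expected to rise over time. Table 53 should therefore be read alongside Table 20.

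A count over multiply imputed visits is an optional sensitivity analysis, not a quick substitute. The 8.4.1 values are unrounded and imputed separately by visit, so simply summing them would not give a 0–3 count and would break ties in the rank test. It would need joint imputation across visits and pooling by Rubin's rules.

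Separately, use one definition of a missing subject in 8.3.10.1 and Table 52 footnote b, and make the title of Table 53 agree with its one-timepoint note. These are wording changes only.
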